## 6.2. Adjustments for Covariates

Additional analyses may be performed on efficacy measures to adjust for factors that may affect survival or disease progression.

All of the patient characteristics listed in Section 6.8 will be considered.

## 6.3. Handling of Dropouts or Missing Data

Patients who are randomized and do not achieve a CR or CRi will be considered as nonresponders in the primary analysis for ORR.

The primary method for handling missing time-to-event data will be censoring.

Partial dates will be imputed, with missing day imputed as 15, and missing month and day imputed as 1-July.

## 6.4. Multicenter Studies

This is a multicenter study. Data collected will be analysed as a whole. Exploratory analyses by individual study sites or country may be conducted as warranted.

## 6.5. Multiple Comparisons/Multiplicity

No adjustment for multiplicity is planned for this study. The primary analysis in phase 2 will compare the ORR for LY3039478 plus dexamethasone and placebo plus dexamethasone.

It is not planned to stop the trial early for efficacy, thus there are no adjustments for multiplicity

## 6.6. Analysis Set Definitions

Efficacy analyses will be based on the **intention-to-treat (ITT)** analysis set. This population is defined as all patients randomized to study treatment.

Patients will be grouped according to dose level cohort (phase 1) or randomized treatment (phase 2). Sensitivity analyses may be conducted (if applicable) excluding patients that are randomized but do not receive treatment, and by actual treatment received.

A secondary analysis of the primary efficacy endpoint in phase 2 based upon the **per-protocol set (PPS)** of patients may be performed if there are significant numbers of patients with major protocol deviations ( $\geq 10\%$  of total patient population). The PPS is defined as those patients in the ITT set who are compliant with the study protocol. The following criteria will be used in the determination of the PPS

- Inclusion/Exclusion criteria not met which may impact efficacy conclusions: Protocol inclusion criteria [1], [2], [3], [4], [5] and protocol exclusion criteria [13], [19], [20], [21].
- Study drug non-compliance as defined in Section 6.10.
- Received incorrect treatment that affects efficacy analysis
- Received prohibited medications whilst on study treatment, including other chemotherapy, other anticancer therapy, immunotherapy, hormonal cancer therapy

(except therapy of hormone-sensitive prostate cancer patients who are stable on GnRH agonist therapy and breast cancer patients who are stable on antiestrogen therapy (eg, an aromatase inhibitor), radiation, surgery for cancer, or experimental medications.

Safety analyses will be based on the **safety analysis set**, defined as all enrolled patients receiving at least 1 dose of any study drug. Patients will be grouped according to actual treatment received.

PD and/or tailoring biomarker analyses will be based on the subset of patients from the above populations from whom a valid assay result (according to laboratory guideline) has been obtained.

## 6.7. Patient Disposition

A detailed description of patient disposition will be provided. It will include a summary of the number and percentage of patients entered into the study, enrolled in the study, and treated as well as number and percentage of patients completing the study, or discontinuing (overall and by reason for discontinuation).

All entered patients will be accounted for in this summary of disposition. Screen failures and patients who died or discontinued before treatment begins will be specified.

A listing of primary reasons for both study treatment and study discontinuation will also be provided according to each randomized treatment arm.

A summary of all important protocol deviations will be provided.

A listing of patients who discontinued due to AE or death from treatment and study itself will also be provided with additional information on cause of death and the AE associated with discontinuation.

## 6.8. Patient Characteristics

Patient demographics including age, sex, screening height, weight and body mass index, race, ethnicity, patient habits (caffeine/alcohol use) and country will be reported using descriptive statistics.

Baseline disease characteristics will be summarized by cohort (phase 1a, phase 1b) or randomized treatment arm (phase 2). Continuous variables will be summarized by median and range, and compared amongst treatment arms by ANOVA. Categorical variables will be summarized by frequency counts and compared amongst treatment arms by Fishers exact test. Statistical comparisons will be provided in phase 2 where data warrant only. The following disease characteristics will be summarized:

- Sex
- Age
- Diagnosis: T-ALL and T-LBL, with T-ALL additionally split by subtype:

TdT+, variable for all of the following: CD1a, CD2, CD3, CD4, CD5, CD7, CD8, CD34

- Pro-T-ALL: cCD3+, CD7+, CD1a-, CD2-, CD4-, CD8-, CD34+/-
- Pre-T-ALL: cCD3+, CD7+, CD1a-, CD2+, CD4-, CD8-, CD34+/-
- Cortical T-ALL: cCD3+, CD7+, CD1a+, CD2+, CD4+, CD8+, CD34-
- Medullary T-ALL: cCD3+, sCD3+, CD7+, CD1a-, CD2+, CD4+or CD8+, CD34-
- ETP T-ALL: Lack of CD1a and CD8 expression, weak CD5 expression with less than 75% positive blasts, and expression of 1 or more of the following myeloid or stem cell markers on at least 25% of lymphoblasts: CD117, CD34, HLA-DR, CD13, CD33, CD11b, and/or CD65
- ECOG status at randomization, or Lanksky status for Phase 1 Part B (pediatrics)
- Disease status: Refractory or relapsed, with relapse additionally split by: first relapse, second relapse, relapse after SCT
- Notch and/or FBWX7 mutational status: Yes, no [See Trinquand et al, 2013 for further details]
- RAS and/or PTEN abnormalities: Yes, no [See Trinquand et al, 2013 for further details]
- Extramedullary disease: Yes, no
- History of CNS leukemia: Yes, no
- Time since initial diagnosis
- Duration of first remission
- Response to last therapy: refractory, or relapsed with duration of remission <1 year, 1-2 years, 2-5 years, >5 years
- Number of prior courses of induction therapy (1, 2, 3, ≥4)
- Country

Other patient characteristics will be summarized as deemed appropriate.

Prior therapies and procedures e.g. stem cell transplant will be listed.

## 6.9. Treatment Compliance

Treatment compliance information for study drug will be collected through pill counts at each visit and the number of tablets taken relative to the number expected to be taken will be summarized.

The patient must take ≥75% of the intended doses to be deemed compliant with study drug administration. Similarly, a patient will be considered significantly noncompliant if he or she is judged by the investigator to have intentionally or repeatedly taken more than the prescribed amount of medication.

Percent compliance is calculated from dispensed and returned capsules as:

$$100 \times (\text{total amount of drug taken (mg)} / \text{total amount of drug prescribed (mg)})$$

Total amount of drug prescribed is the sum of products of dosing intervals and the expected dose for each interval. Total dose prescribed should take into consideration any dose adjustment(s) before treatment discontinuation date. Treatment compliance will be summarized for LY3039478 and Dexamethosone separately by randomized treatment, cycle, and overall.

## 6.10. Concomitant Therapy

All medications will be coded to the generic preferred name according to the current World Health Organization (WHO) drug dictionary. All concomitant medications listings will include both the term reported in CRF and the WHO dictionary term and if concomitant medication use is due to adverse event (AE), the associated AE will also be listed. A separate listing of transfusions will be created.

Anti-cancer systemic therapy, radiotherapy and surgery that occurs post discontinuation of study treatment is captured separately from concomitant medication as the existence of such therapies can lead to censoring of time to event endpoints. Patients that received post discontinuation therapies will be listed by treatment arms.

## 6.11. Efficacy Analyses

Efficacy analyses will be conducted on the ITT analysis set, with patients grouped according to randomized treatment.

The following are definitions of the primary and secondary efficacy endpoints:

### Primary Endpoint:

**Overall Response Rate (ORR)** is defined as the proportion of patients who achieved a best overall response of either complete remission (CR) or incomplete remission (CRI). The ORR (CR and CRI) is the sum of patients achieving a CR or a CRI divided by the total number of patients randomized in that arm.

### Secondary Endpoints:

- **Partial Response (PR)** is defined as the proportion of patients who achieved a best overall response of partial remission (PR), out of the total number of patients randomized in that arm.
- **Complete Remission (CR)** is defined as the proportion of patients who achieved a best overall response of complete remission (CR), out of the total number of patients randomized in that arm.
- **ORR and PR** is defined as the proportion of patients who achieved a best overall response of either complete remission (CR), incomplete remission (CRI) or partial remission (PR), out of the total number of patients randomized in that arm.

All of the above endpoints (ORR, PR, CR, ORR and PR) will also be calculated for those patients that cross-over in the Phase 2 part of the trial and receive LY3039478 plus dexamethasone after failure of placebo plus dexamethasone.

- **Overall Survival (OS)** is defined for all patients in the trial, and measured from the date of study enrollment to the date of death from any cause. OS duration is measured from the date of randomization to the date of death from any cause in the Phase 2 portion of the study. For each patient who is not known to have died as of the data-inclusion cutoff date for a particular analysis, OS will be censored for that analysis at the date of last contact prior to the

data inclusion cutoff date (contacts considered in the determination of last contact date include AE date, lesion assessment date, visit date, and last known alive date).

- **Relapse Free Survival (RFS)** is defined only for patients who achieve CR/CRI.

For T-ALL, RFS is measured from the date of attaining the leukemia-free state until the date of T-ALL relapse or death from any cause, whichever occurs first. Relapsed disease for T-ALL is defined as the reappearance of the blast in the blood or bone marrow (>5%) or any extramedullary site after achievement of a CR.

For T-LBL, RFS is measured from the time of occurrence of a disease-free state or attainment of a CR to disease recurrence or death as a result of lymphoma or acute toxicity of treatment.

For a patient who is not known to have relapsed or died by the end of study follow-up, observation of RFS is censored at the date of last contact prior to the data inclusion cutoff, at which an adequate assessment was completed, i.e. blood or bone marrow samples, CT-MRI or PET assessment.

- **Event Free Survival (EFS)** is defined for all patients and measured from the date of entry on study. It is measured until treatment failure, relapse from CR, or death from any cause, whichever occurs first.

For T-ALL, treatment failure is defined by progressive disease, which is an increase of at least 25% in the absolute number of circulating or bone marrow blasts or development of extramedullary disease. For T-ALL patients with preexisting mediastinal disease, progressive disease is defined by a greater than 25% increase in the sum of the product of the greatest perpendicular diameters (SDP) of the mediastinal enlargement.

For T-LBL, treatment failure is defined as relapsed or progressive disease in protocol Table JJCB.10.1.

For a patient with none of these events before the end of study follow-up, observation of EFS is censored at the date of last contact prior to the data inclusion cutoff date, at which an adequate assessment was completed i.e. blood or bone marrow samples, CT-MRI or PET assessment. If the patient does not achieve a CR, EFS is defined as the point of treatment failure or death, whichever comes first.

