## 6. A Priori Statistical Methods

### 6.1. General Considerations

Phase 1 Part A, Phase 1 Part B and Phase 2 study parts will be reported in separate TFLs.

Results of descriptive analyses and estimates from inferential analyses will be presented by dose level cohort (phase 1) or by treatment (phase 2). In the phase 2 study part, an additional group will be included in primary efficacy and safety TFLs to represent data for patients receiving LY3039478 in combination with dexamethasone after failure of placebo in combination with dexamethasone.

All tests of treatment effects will be conducted at a 2-sided alpha level of 0.05, unless otherwise stated. All tests of interactions will be conducted at a 2-sided alpha level of 0.1, and all CIs will be given at a 2-sided 95% level, unless otherwise stated.

The assumptions for each statistical method will be evaluated. If there is violation of assumptions, alternative statistical methods may be used.

Additional exploratory analyses of the data will be conducted as deemed appropriate.

For continuous variables, summary statistics will include number of patients, mean, median, standard deviation, minimum, and maximum. Categorical endpoints will be summarized using number of patients, frequency, and percentages. Any missing longitudinal data will not be imputed, rather estimated from an appropriate random mixed effects model. Transformations will be applied where assumptions behind any analysis are better satisfied by data being transformed onto an alternative scale. All results from any of these analyses will be back transformed to the original scale. Alternatively, nonparametric methods will be applied.

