#### **Time to Event Endpoints**

For the secondary efficacy endpoints OS, RFS, and EFS, the Kaplan-Meier method (Kaplan and Meier 1958) will be used to estimate the survival curves as well as survival rates at various

prespecified time points (12 months for OS, 6 and 12 months for RFS and EFS) for each treatment arm.

The secondary efficacy endpoint DoR is subject to competing risk of death without relapse; therefore, the cumulative incidence of relapse (Gray 1988; Pepe and Mori 1993; Gooley et al. 2001) will be used. In the calculation, patients who did not have the event will be considered right-censored observations.

The comparison of the survival curves between treatment groups will be conducted by a log-rank test. Exploratory analyses for the comparison of the survival curves between treatment groups may additionally be conducted by a stratified log-rank test with some of the following stratification variables: initial diagnosis (T-ALL phenotype, T-LBL), response to last therapy (refractory or relapsed), age, number of prior therapies ( $\leq 2$ ,  $> 2$ ), NOTCH-1/FBXW7/RAS/PTEN status.

The Cox proportional hazard model (Cox 1972) with treatment as a factor will be used to estimate the hazard ratio and corresponding 95% CI with Wald's test p-value after adjusting for the following potential predictive/prognostic variables: initial diagnosis (T-ALL phenotype, T-LBL), response to last therapy (refractory or relapsed), age, number of prior therapies ( $\leq 2$ ,  $> 2$ ), NOTCH-1/FBXW7/RAS/PTEN status.

The unadjusted impact of patient baseline disease characteristics listed in Section 6.8 on OS and EFS will be explored using Cox proportional hazard models (Cox 1972) with the baseline characteristic as a factor (continuous variables split at median) and the hazard ratio and corresponding 95% CI plotted on a forest plot. Any characteristics found to be significant prognostic markers for EFS or OR may be included as additional covariates in COX proportional hazard model analyses to compare treatment arms.

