#### **6.11.4. Sensitivity Analyses**

For the analysis of time-to-event endpoints EFS and RFS, sensitivity analysis definitions as described in table JJCB.6.2 will be completed for the log-rank test. Such analyses will only be conducted if the primary analysis of such endpoints warrants sensitivity analysis to evaluate whether and to what extent the conclusion would be affected under the different censoring rules.

For the analysis of OS, sensitivity analysis definition SA1 as described in Table JJCB.6.2 will also be completed. Further analyses may explore OS adjusting for patients which received LY3039478 plus dexamethasone following treatment failure of placebo plus dexamethasone, if warranted.

Additionally, analyses may be conducted (if applicable) excluding patients that are randomized but do not receive treatment, and by actual treatment received.

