One futility interim analysis is planned in Phase 2 once 30 patients are randomized and have completed the CR status determination. PK and/or PD data, if available, will also be reviewed at this interim analysis. Given the small sample size per treatment arm at the interim analysis: n=10 for the placebo plus dexamethasone (control) arm, and n=20 for the LY3039478 plus dexamethasone (test) arm, and the low anticipated ORR for the control arm ( $\leq 5\%$ ) in this study, no formal inferential analysis is planned at the interim analysis. The AC may recommend to stop the study for futility if the observed improvement in response rates is less than 5%. For example, if the control arm has 1 response in 10 patients (10%), the test arm would need to observe at least 3 responses in 20 patients (15%) to warrant continuing the study. This decision criterion is

provided to the AC for guidance only. Any recommendation to stop for futility will be based on AC review of all available safety and efficacy data in addition to ORR rate.

Simulations have been conducted in order to understand the operating characteristics of the futility rule and the impact on statistical power is considered minimal. It is not planned to stop the trial early for efficacy, thus there are no adjustments for multiplicity.

Only the assessment committee is authorized to evaluate unblinded interim efficacy and safety analyses. Study sites will receive information about interim results ONLY if they need to know for the safety of their patients.

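### RFS exists only for responders (16 v 1 expected), yet the SAP compares it between arms by log-rank test and adjusted Cox model as if it were a randomized comparison

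*SAP*

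**What the plan says.** Under Secondary Endpoints in SAP 6.11, RFS "is defined only for patients who achieve CR/CRI". The protocol's T-ALL definition (10.1.3.1) is narrower and admits CR only.

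Under Time to Event Endpoints (SAP 6.11.3), OS, RFS and EFS are named together for Kaplan-Meier estimation. The section continues: "The comparison of the survival curves between treatment groups will be conducted by a log-rank test". A Cox model adjusted for five baseline variables "will be used to estimate the hazard ratio and corresponding 95% CI", with a Wald p-value. Neither sentence excepts RFS. SAP 6.11.4 confirms that RFS is meant: "For the analysis of time-to-event endpoints EFS and RFS, sensitivity analysis definitions as described in table JJCB.6.2 will be completed for the log-rank test". The sentence after that makes these sensitivity analyses conditional on the main analysis calling for them.

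On the analysis set, SAP 6.11 states: "Efficacy analyses will be conducted on the ITT analysis set, with patients grouped according to randomized treatment". Protocol 12.2.8 goes further and places every randomized patient in the analysis of these endpoints. DoR, another responder-only endpoint, falls under the same statements.

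The SAP is more cautious elsewhere. At the 20 v 10 interim (6.17) it cites the small arms and "the low anticipated ORR for the control arm", and says "no formal inferential analysis is planned at the interim analysis".

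**The concern.** Response is an outcome of treatment, and the plan expects it to differ eightfold between arms. The patients who enter an RFS comparison are therefore two differently selected groups, and randomization no longer balances them. The control group may also be empty or hold a single patient. A log-rank p-value and an adjusted hazard ratio reported beside those for OS and EFS invite the reader to see a treatment effect on durability of remission. The comparison cannot support that reading, and no multiplicity adjustment (SAP 6.5) limits how many such p-values appear.

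**Working it through.** **Inputs.** Planned ORR 40% v 5% and 40 v 20 patients (SAP 5.2); control ORR anticipated at no more than 5% (SAP 6.17); RFS population CR/CRi (SAP 6.11). Under the protocol's CR-only definition the counts could only be lower.

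**The plan's own figure.** No event count or power is given for RFS. The only stated power is about 82% for ORR. Exact enumeration of the two-sided Fisher test at 40 v 20 gives 87.8% (87.7% with the futility rule), or 85.6% with a doubled one-sided p. The stated value is not reproduced, but it is conservative and nothing below depends on it.

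**1. Responders.** Expected: 40 x 0.40 = 16 and 20 x 0.05 = 1. P(no control responder) = 0.95^20 = 0.358. P(at most one) = 0.358 + 20 x 0.05 x 0.95^19 = 0.736. Other control rates are assumptions:

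| Control ORR | P(0) | P(at most 1) |
|---|---|---|
| 2.5% | 60% | 91% |
| 5% (planned) | 36% | 74% |
| 10% | 12% | 39% |

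**2. Type I error of the asymptotic log-rank test, all events observed.** At 16 v 1 the statistic depends only on the rank of the one control event. It is 16.0 at rank 1, 6.78 at rank 2, 3.74 at rank 3 and 3.21 at rank 17. Only ranks 1 and 2 exceed 3.84, so the error is 2/17 = 11.8% against a nominal 5%. Letting the responder counts vary, both arms have a responder with probability 0.642. Given that, the rejection rate is about 12% (11.7% by simulation, 12.5% on a separate calculation). Over all trials, counting those with no test as non-rejections, it is about 0.642 x 0.125 = 8%.

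**3. Exact test.** The smallest permutation p-value is 1/C(n1+n0, n0). At 16 v 1 that is 1/17 = 0.059. With one control responder, 19 test-arm responders are needed to reach 1/20 = 0.05. Summed over Bin(40, 0.40) and Bin(20, 0.05), p <= 0.05 is attainable in 34% of trials.

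**4. Power (Schoenfeld, assumed HR 0.5).** With 17 events at 16:1, z = 0.693 x sqrt(17 x 1/17 x 16/17) = 0.672, so power is Phi(0.672 - 1.960) = 9.9%. Reaching 80% would need (1.960 + 0.842)^2 / (0.0554 x 0.480), about 296 events. For comparison, EFS in all 60 patients at 2:1 gives z = 0.693 x sqrt(60 x 2/9) = 2.53 and power 71.6%; with 45 events it is 59.2%.

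**5. Cox model.** Treatment 1, diagnosis 1 or 5, last response 1, age 1, prior therapies 1, mutation status 1 or 2: 6 to 11 terms for about 17 events at most.

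**6. Direction of selection bias (assumed and unadjusted).** Suppose treatment does not affect relapse, 5% of patients respond on either arm, a further 35% respond only on LY3039478, and those extra responders relapse at h times the rate of the others. With complete follow-up the crude relapse rate ratio is 40/(5 + 35/h). For h = 2 it is 40/22.5 = 1.78. For h = 0.5 it is 40/75 = 0.53. Selection alone can favour either arm.

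**The case against.** RFS is one of several secondary endpoints, its objective is to assess and not to compare, and ORR carries the trial. This stands and limits the severity, but 6.11.3 still prescribes a p-value and a hazard ratio.

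The SAP has a safety clause: "If there is violation of assumptions, alternative statistical methods may be used". It is optional and triggered by violated model assumptions. It does not address selection after randomization.

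The required confidence interval would warn the reader. At 16 v 1 with all events, SE(log HR) = sqrt(1/16 + 1/1) = 1.03, so the interval spans a factor of exp(1.96 x 1.03), about 7.5, each way. This is fair, but an interval that wide is itself a reason not to plan the estimate, and it does not show selection bias.

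Several stronger readings are tempting and are not supported:

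- *Non-responders would be forced into RFS by the ITT wording.* The RFS definition keeps them out, so this is a wording conflict. The explicit all-randomized sentence is in protocol 12.2.8. The SAP has only its general ITT line in 6.11.
- *The RFS sensitivity log-rank tests are mandatory.* SAP 6.11.4 makes them conditional.
- *The error rate is 11.8% whatever happens.* That figure belongs to exactly 16 v 1.
- *The RFS hazard ratio will be biased against LY3039478 by a known amount.* The documents give no basis for a size or a direction, and the planned Cox model is covariate-adjusted.
- *EFS is invalid too.* EFS is defined for all patients. Its wording conflicts affect only how some dates are derived.

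**Conclusion.** The concern holds for RFS. The plan prescribes between-arm inference on a group defined by a post-randomization outcome, with 16 v 1 patients expected. In 36% of trials no comparison is possible. Otherwise the asymptotic test is miscalibrated (about 12% when both arms have responders, about 8% over all trials), the exact test usually cannot reach significance, and power is about 10% at a hazard ratio of 0.5. The counts rest on the plan's response rates. The error rates and power also assume that all events are observed, and the hazard ratio is assumed. The size of any selection bias is not established.

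This should be changed before unblinding. It does not touch the primary ORR analysis or invalidate EFS or OS. The three lesser wording conflicts listed with the fix are minor clarifications.

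**What to change.** In SAP 6.11.3 and 6.11.4, report RFS descriptively by arm: number of responders, number of events, Kaplan-Meier where numbers allow, and otherwise a listing of individual durations. Give no RFS log-rank p-value or Cox hazard ratio. Keep EFS and OS as the randomized time-to-event comparisons.

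State one RFS population, CR or CR/CRi, with a matching relapse definition; the T-ALL relapse wording now refers to CR alone. Exempt RFS and DoR from the ITT line in SAP 6.11 and from the all-randomized sentence in protocol 12.2.8.

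Clarify in the same edit:

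- (a) T-ALL RFS counts any death, while T-LBL RFS counts only death from lymphoma or acute toxicity. The SAP carries both over from protocol 10.1.3.1 and 10.1.3.2. Reconcile them and say how other T-LBL deaths are handled, since the RFS censoring sentence does not cover them.
- (b) State randomization as the Phase 2 EFS origin. EFS now runs from study entry, Table JJCB.6.1 defines Entered by consent, and Table JJCB.6.2 uses randomization.
- (c) Add PR to the list of adequate determinations under Censoring Rules for EFS and RFS, or delete the list. Read literally, every consecutive PR assessment is skipped, so a patient in ongoing PR would be censored for EFS at the last non-PR assessment, or at randomization if there is none. The loss is not limited to one assessment interval.

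The cost is SAP wording and programming, with no new data. Protocol 12.2.1 requires an amendment only for a principal feature, so the departure from 12.2.8 can be described in the study report or aligned at the next amendment. What is lost is an RFS p-value that could not be interpreted.

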10.1.3.2. T-LBL

For T-LBL followed by CT scan/MRI: PR is defined as a reduction of $\geq 50\%$ in the sum of the products of the perpendicular diameters of all measurable lesions compared with pretreatment measurements. No new lesions will appear, and no existing lesions will enlarge. Stable disease (SD) is defined as a <50% reduction and no more than a 25% increase in the sum of the products of 2 perpendicular diameters of all measured lesions, and the appearance of no new lesions (Cheson et al. 2007).

Two consecutive determinations of PR before progression, but not qualifying for a CR, are required for a best response of PR for T-LBL patients being followed by CT. Best response of SD is defined as disease that does not meet the criteria for CR, PR, or progressive disease.

For T-LBL followed by PET-CT scan, the criteria for PR is as follows: partial metabolic response and a score of 4 or 5 with reduced uptake compared with baseline and residual masses of any size in the lymph nodes or extralymphatic sites. There can be no new lesions and residual uptake higher than uptake in normal marrow but reduced compared with baseline (diffuse uptake compatible with reactive changes from chemotherapy allowed). If there are persistent focal changes in the marrow in the context of a nodal response, consideration should be given to further evaluation with MRI or biopsy or an interval scan (Cheson et al. 2014).

DoR for T-LBL is measured from the time when criteria for response (ie, CR or PR) are met, until the first documentation of relapse or progression. For patients who die without report of relapse, DoR is censored on the date of death, regardless of cause. For a patient with no report of relapse or death by the end of the follow-up data collection, observation is censored at the date of last contact prior to the data inclusion cutoff date.

RFS for T-LBL is measured from the time of occurrence of a disease-free state or attainment of a CR to disease recurrence or death as a result of lymphoma or acute toxicity of treatment. For a patient who is not known to have relapsed or died by the end of study follow-up, observation of RFS is censored at the date of last contact prior to the data inclusion cutoff date.

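### RFS counts any death for T-ALL but only some deaths for T-LBL, pools both diagnoses by arm, and gives no rule for other T-LBL deaths in remission

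*SAP*

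**What the plan says.** SAP 6.11 (Secondary Endpoints) defines RFS separately for the two diseases. For T-ALL it runs "until the date of T-ALL relapse or death from any cause, whichever occurs first". For T-LBL it runs from a disease-free state or CR to recurrence or "death as a result of lymphoma or acute toxicity of treatment". The protocol makes the same split. Section 10.1.3.1 counts any death for T-ALL, and 10.1.3.2 follows T-LBL patients "to disease recurrence or death as a result of lymphoma or acute toxicity of treatment". The SAP has therefore inherited the difference; it is not a slip in one document.

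In the SAP a single censoring sentence serves both diseases: "For a patient who is not known to have relapsed or died by the end of study follow-up, observation of RFS is censored", at the last contact that had an adequate disease assessment.

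The analysis does not separate the diagnoses. SAP 6.11.3 (Time to Event Endpoints) plans Kaplan-Meier curves with rates at "prespecified time points (12 months for OS, 6 and 12 months for RFS and EFS) for each treatment arm", and then: "The comparison of the survival curves between treatment groups will be conducted by a log-rank test". Protocol 12.2.8 plans the same.

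Two neighbouring endpoints have no such gap. Event-free survival (EFS) counts death from any cause in both diseases. Duration of response (DoR) states what happens to a patient who dies without a reported relapse, whatever the cause.

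**The concern.** One endpoint name covers two different events, and patients with either event definition enter the same curve. A pooled 6- or 12-month RFS rate is then neither freedom from relapse and all death, nor freedom from relapse and disease- or treatment-related death. What it measures depends on the mix of diagnoses.

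There is also a hole. A T-LBL patient in remission who dies of, say, an unrelated illness has no listed event. The censoring sentence does not apply either, because the patient is known to have died. The analyst could count the death, censor at the date of death, censor at the last adequate assessment, or treat it as a competing risk. These choices give different estimates.

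For T-LBL the cause of death also becomes decisive. The documents do not define acute toxicity for this purpose. They do not say whether treatment includes later therapy such as a transplant, or who classifies the death. Transplants are foreseen (protocol 12.2.5 and 12.2.8; SAP Table JJCB.6.2, SA 1), so deaths that are hard to classify can be expected.

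**Working it through.** The documents give no event count, hazard ratio or power for RFS, so there is no stated figure to reproduce. The check is mainly textual, with arithmetic to bound the size.

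**Step 1. How a death in remission is handled**

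| Endpoint | T-ALL | T-LBL: lymphoma or acute toxicity | T-LBL: any other cause |
|---|---|---|---|
| RFS | event | event | not an event, and no censoring rule |
| EFS | event | event | event |
| DoR | censored at death | censored at death | censored at death |

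**Step 2. Does another section supply the rule?**

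- SAP 6.3 makes censoring the method for missing time-to-event data. A known death is not missing.
- The text under Censoring Rules for EFS and RFS deals with which assessment date to use and what counts as adequate.
- Table JJCB.6.2 lists sensitivity definitions only, and SAP 6.11.4 runs them for RFS only if the primary analysis warrants it. SA 1 and SA 2 refer to death with no limit by cause or diagnosis, which does not match the T-LBL definition.

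None of these closes the gap.

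**Step 3. Direction.** If the deaths are counted as events, there is no upward bias. If they are censored or ignored, the curve omits a step down, so T-LBL RFS and pooled RFS can only be higher.

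**Step 4. Size of the RFS set.** SAP 5.2 assumes ORR of 40% in 40 patients and 5% in 20 patients: 0.40 × 40 = 16 and 0.05 × 20 = 1, so about 17 responders. The T-LBL share is not stated. At an assumed 20% to 40%, T-LBL responders number 0.20 × 17 = 3.4 to 0.40 × 17 = 6.8, or about 3 to 7.

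**Step 5. Effect of one death.** Take the 16 expected LY3039478 responders with no earlier censoring, and let n be at risk just before the death. The curve stands at n/16. Counted as an event, the death lowers it to (n − 1)/16; censored, it stays at n/16. The difference at that time is 1/16 = 6.25 points. Afterwards both versions have the same risk set and are multiplied by the same factors, so the gap can only shrink. A death after the 6- or 12-month landmark does not change that landmark.

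**Step 6. Illustration at 12 months.** The hazards are assumptions, the same for both diagnoses: 0.08 per month for relapse, lymphoma death or toxicity death, and h per month for other death. T-LBL RFS is exp(−12 × (0.08 + h)) if other deaths are events, and exp(−12 × 0.08) = 38.3% if they are censored. The pooled difference is taken as the T-LBL share times the T-LBL difference.

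| h | Counted | Censored | T-LBL difference | Pooled, 20% share | Pooled, 40% share |
|---|---|---|---|---|---|
| 0.01 | 34.0% | 38.3% | 4.3 points | 0.9 | 1.7 |
| 0.02 | 30.1% | 38.3% | 8.2 points | 1.6 | 3.3 |
| 0.04 | 23.7% | 38.3% | 14.6 points | 2.9 | 5.8 |

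The range is about 1 to 6 points. The weighted average slightly overstates a true pooled Kaplan-Meier difference at the top end. With h = 0.04 and a 40% share, the pooled hazard is 0.12 − 0.40 × 0.04 = 0.104, giving exp(−12 × 0.104) = 28.7% and a difference of 28.7 − 23.7 = 5.0 points.

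**The case against.** The case for leaving the plan alone has some force.

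- **Disease-specific definitions can be deliberate.** The protocol uses separate response criteria for the two diseases, and both documents agree on the split. This stands as an explanation, but it does not justify pooling the two or leaving one group of deaths without a rule.
- **Diagnosis is not ignored.** It is a covariate in the planned Cox model and an exploratory subgroup. For stratification, "Exploratory analyses for the comparison of the survival curves between treatment groups may additionally be conducted by a stratified log-rank test", with diagnosis among the candidate strata. Adjusting for diagnosis does not reconcile two event definitions.
- **No death is lost from the efficacy evaluation.** OS and EFS count every death in both diseases. This is correct and limits the harm.
- **Cause-of-death data are planned.** Reasons for death are summarised by period (SAP 6.14.3), and investigators assess the relatedness of adverse events (protocol 10.3.1). What is missing is the rule that turns this information into an RFS event. Some deaths, such as a fatal infection on treatment, might already qualify as acute toxicity.
- **Transplants are partly handled.** SA 1 censors at transplant, but only as a sensitivity analysis.
- **The RFS comparison is weak under any definition,** with about one expected responder on control. This stands, and it bears on priority.

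A reader might infer that the sponsor will choose the handling after seeing the deaths. The documents do not show that: protocol 12.2.1 lets clarifications be written into the SAP before the aggregate database is unblinded.

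**Conclusion.** The point holds. RFS has two death components under one name, both feed one curve per arm, and T-LBL deaths in remission from other causes have no primary-analysis rule.

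Two stronger readings should be avoided. A reader might infer that the plan overstates RFS. It does so only if these deaths are censored or ignored, and because no rule is given, that outcome is not fixed. A reader might also take 6 points as the expected bias. The 1/16 figure is the most that one death can shift the curve under Step 5's conditions. The documents give neither the T-LBL share nor any expected number of such deaths. The 1 to 6 point range rests on the assumed shares and hazards, and on censoring these deaths.

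The consequence is limited to a secondary endpoint in about 17 expected responders. ORR is unaffected. The change is worth making because the plan, followed as written, yields a mixed endpoint and the repair is simple.

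**What to change.** In SAP 6.11 and protocol 10.1.3.2, define the T-LBL RFS event as recurrence or death from any cause, whichever comes first. This matches T-ALL RFS and the EFS death component, makes the existing censoring sentence complete, fits the unrestricted mention of death in SA 1 and SA 2, and removes the need to classify cause of death for this endpoint.

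The cost is one sentence in each document. No new data are needed, because death dates are already collected for OS. Both documents should change together so that they stay aligned, before the aggregate database is unblinded.

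If the sponsor prefers a cause-specific RFS for T-LBL, the alternative is to report RFS by diagnosis. The SAP would then state whether other deaths are censored (and at which date) or treated as a competing risk, define acute toxicity, and say who classifies each death. That costs more text and an attribution process.
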